4.2.2 Exclusion Criteria

- Type 1 diabetes mellitus
- History of diabetic ketoacidosis or hyperosmolar nonketotic coma
- Hemoglobinopathies with low hematocrit (hematocrit below normal limits that may impair exercise tolerance) or abnormal CBC
- History of pancreatitis, or cancer (except basal cell carcinoma)
- Previous coronary or cerebrovascular event within 6 months of screening or active or clinically significant coronary and/or peripheral vascular disease

- Statin use started (or dose change) in the last 3months,
- Daily use of oral or injectable anti-diabetic medication other than Metformin
- use of any form of steroid medication (oral, inhaled, injected or nasal) within the last 3 months
- Systolic BP> 140 mmHg and Diastolic BP> 90mmHg at screening visit.
- Active wounds or recent surgery within 3 months
- Inflammatory disease, or current use of anti-inflammatory drugs
- Untreated hyper/hypothyroidism
- Contraindications for moderate exercise
- Implanted devices (e.g., pacemakers) that may interact with Tanita scale

Physical and Laboratory Test Findings

- Pre-existing liver disease and/or ALT and AST >2.5X's UNL,
- serum creatinine levels ≥ 1.5 mg/dL for men, ≥ 1.4 mg/dL for women, estimated CrCl ≤ 50 mL/min)
- Triglycerides >400 mg/dL

Allergies and Adverse Drug Reactions

- Subjects with a history of any serious hypersensitivity reaction to saxagliptin or DPP-4 inhibitor.

Sex and Reproductive Status

- WOCBP who are unwilling or unable to use an acceptable method to avoid pregnancy for the entire study period.
- Women who are pregnant or breastfeeding.

See Section on WOCBP above (Section 4.2.1, item # 3.)

Prohibited Treatments and/or Therapies

- Treatment with systemic cytochrome P450 3A4 (CYP 3A4) inhibitors

Other Exclusion Criteria

- Prisoners or subjects who are involuntarily incarcerated.
- Subjects who are compulsorily detained for treatment of either a psychiatric or physical (e.g., infectious disease) illness.

Additionally, patients who are active smokers, patients who are pregnant, nursing women, and post menopausal women who are on hormone replacement therapy will be excluded. Patients on low dose oral contraceptives will be allowed to participate as these formulations contain lesser amount of estrogens.

Eligibility criteria for this study have been carefully considered to ensure the safety of the study subjects and to ensure that the results of the study can be used. It is imperative that subjects fully meet all eligibility criteria.

4.2.3 Discontinuation of Subjects from Treatment

Subjects MUST discontinue investigational product (and noninvestigational product at the discretion of the investigator) for any of the following reasons:

- Withdrawal of informed consent (subject's decision to withdraw for any reason).
- Any clinical adverse event, laboratory abnormality, or intercurrent illness which, in the opinion of the investigator, indicates that continued participation in the study is not in the best interest of the subject.
- Changes in estimated CrCL to ≤ 50 mL/min necessitating reduction in saxagliptin dose
- Treatment with systemic cytochrome P450 3A4 (CYP 3A4) inhibitors necessitating reduction in saxagliptin dose
- Pregnancy
 - Instruct WOCBP to contact the investigator or study staff immediately if they suspect they might be pregnant (e.g., missed or late menstrual period) at any time during study participation. Institutional policy and local regulations should determine the frequency of on-study pregnancy tests for WOCBP enrolled in the study.
 - The investigator must immediately notify BMS if a study subject becomes pregnant.
- Loss of ability to freely provide consent through imprisonment or involuntary incarceration for treatment of either a psychiatric or physical (e.g., infectious disease) illness.

All subjects who discontinue should comply with protocol-specified follow-up procedures outlined in Section 6. The only exception to this requirement is when a subject withdraws consent for all study procedures or loses the ability to consent freely (i.e., is imprisoned or involuntarily incarcerated for the treatment of either a psychiatric or physical illness). If a subject withdraws before completing the study, the reason for withdrawal must be documented appropriately.

5 TREATMENTS

5.1 Study Treatment: Saxagliptin

Definition of Investigational Product: A pharmaceutical form of an active substance or placebo being tested or used as a reference in a clinical study, including products already with a marketing authorization but used or assembled (formulated or packaged) in a way different from the authorized form, or used for an unauthorized indication, or when used to gain further information about the authorized form. In this protocol, the investigational product is saxagliptin.

Definition of Non-Investigational Product: Other medications used in the study as support or escape medication for preventative, diagnostic, or therapeutic reasons as components of a given standard of care. In this protocol, the non-investigational product is Metformin. Patients will continue on Metformin as per their study entry dose added to Saxagliptin or placebo. Metformin is not an investigational drug and will not be provided by AstraZeneca Pharmaceuticals LP Bristol Myers Squibb. Subject will obtain continue to obtain Metformin as they did prior to study entry.

5.1.1 Identification

Saxagliptin 5 mg tablets are pink, biconvex, round, film-coated tablets with “5” printed on one side and “4215” printed on the reverse side, in blue ink.

5.1.2 Packaging and Labeling

Saxagliptin film-coated tablets in strengths of 1 mg, 2.5 mg, 5 mg, and 10 mg (as the free base) have been developed. The tablets are manufactured from saxagliptin and inactive ingredients including lactose, microcrystalline cellulose, croscarmellose sodium, magnesium stearate, and film-coating materials (Opadry® II white and Opadry® II yellow). The tablets are supplied in high-density polyethylene bottles containing two desiccant and charcoal canisters, with cotton coil and tightly closed with a child resistant cap.

5.1.3 Handling and Dispensing

The investigational product should be stored in a secure area according to local regulations. The investigator is responsible for ensuring that it is dispensed only to study subjects and only from official study sites by authorized personnel, as dictated by local regulations.

The investigator is responsible for ensuring that the investigational product is stored under the appropriate environmental conditions (temperature, light, and humidity), as described below:

Saxagliptin tablets should be stored at temperatures between 15°C and 20°C (59°F and 77°F) in tightly closed containers. If concerns regarding the quality or appearance of the investigational product arise, do not dispense the investigational product, and contact BMS immediately.

5.2 Drug Ordering and Accountability

5.2.1 Initial Orders

Contact the BMS protocol manager for information.

5.2.2 Re-Supply

Contact the BMS protocol manager for information.

5.3 Method of Assigning Subjects to a Treatment

Subjects, as per selection criteria below will be randomized to treatments using a permuted block design, developed by the Epidemiology & Biostatistics Research Core. This approach ensures groups will be approximately balanced at any time during the study and at study completion.

5.4 Selection and Timing of Dose for Each Subject

The recommended dose of saxagliptin is 5 mg PO will be given once daily. Saxagliptin can be taken with or without food.

5.4.1 Dose Modifications

A single dosage adjustment to 2.5 mg daily is recommended for patients with moderate or severe renal impairment, or with end-stage renal disease ($\text{CrCl} \leq 50 \text{ mL/min}$, approximately corresponding to serum creatinine levels of $\geq 1.7 \text{ mg/dL}$ in men and $\geq 1.5 \text{ mg/dL}$ in women). Assessment of renal function is recommended before initiation of saxagliptin, and periodically thereafter. Given that this study protocol includes only saxagliptin 5 mg dose, the participation of any study subject requiring dose adjustment while on study medication will be discontinued (see section 4.2.3.).

5.5 Blinding/Unblinding

Blinding is critical to the integrity of this clinical study. However, in the event of a medical emergency or pregnancy in a subject, **in which knowledge of the investigational product is critical to the subject's management**, the blind **for that subject** may be broken.

Before breaking the blind of an individual subject's treatment, the investigator should have determined that the information is necessary, i.e., that it will alter the subject's immediate management. In many cases, particularly when the emergency is not investigational product-related, the problem may be properly managed by assuming that the subject is receiving active product without the need for unblinding.

5.6 Concomitant Treatments

5.6.1 Prohibited and/or Restricted Treatments

Ketoconazole significantly increased saxagliptin exposure. Similar significant increases in plasma concentrations of saxagliptin are anticipated with other strong cytochrome P450 3A4/5 (CYP3A4/5) inhibitors. The dose of ONGLYZA should be limited to 2.5 mg when coadministered with a strong CYP3A4/5 inhibitors (e.g., ketoconazole, atazanavir, clarithromycin, indinavir, itraconazole, nefazodone, neflifavir, ritonavir, saquinavir, and telithromycin).

Given that this study protocol includes only saxagliptin 5 mg dose the participation of any study subject requiring dose adjustment while on study medication will be discontinued (see section 4.2.3.).

5.6.2 Other Restrictions and Precautions

Saxagliptin should not be used in patients with type 1 diabetes mellitus or for the treatment of diabetic ketoacidosis.

5.7 Treatment Compliance

Subjects will be given study drug at each dispensing visit with enough study drug to last until the next visit. The subjects will return all unused medication and compliance will be assessed. Subjects will be in compliance if they have taken at least 75% of study drug.

6 STUDY ASSESSMENTS AND PROCEDURES

6.1 STUDY SCHEMATIC

6.2 TIME AND EVENTS SCHEDULE

Time and Events Schedule for Protocol

Procedure	Screening Visit (Week -4)	Baseline/ Randomization Visit 1 (Week 0)	During Treatment Visit 2 (Week 6)	End-of-Treatment Visit 3 (Week 12)
Eligibility Assessments				
Informed Consent		X		
Inclusion/Exclusion Criteria		X		
Medical History		X		
Safety Assessments				
Physical Examination	X			X
Targeted Physical Examination		X	X	X

Time and Events Schedule for Protocol

Procedure	Screening Visit (Week -4)	Baseline/ Randomization Visit 1 (Week 0)	During Treatment Visit 2 (Week 6)	End-of-Treatment Visit 3 (Week 12)
Vital Signs (BP, RR, Temp, HR)	X	X	X	X
Assessment of Signs and Symptoms		X	X	X
Adverse Events Assessment	X	X	X	X
Laboratory Tests (Biochemical)	screening	X	X	X
Pregnancy Test (if applicable)	X	X	X	X
Efficacy Assessments				
Peripheral blood draw for CD34+cell harvest		X	X	X
Pulse wave analysis		X	X	X
Pulse wave velocity assessment		X	X	X
Hip / Waist Measurements		X	X	X
Tanita Scale		X	X	X
REE		X	X	X
Clinical Drug Supplies				
Randomize		X		
Dispense Study Treatment		X	X	

Screening visit= week-4; Visit 1= week 0, Visit 2= week 6 and Visit 3= week 12.

+/- 3 day window for visits 1-3

Research Study Design and Methods:

Patient Definition and Selection: Adults aged 40-70 years will be recruited mainly from the MFA research patient database provided by MFA Information Technology. The remaining patients will be recruited from the endocrinology clinic at GWU and referring primary care physicians. Suitable advertisements for the study patient enrollment will be posted. Patients will be included in the study if they have been diagnosed with type 2 diabetes within the previous 8 years using criteria of the American Diabetes Association², and are currently treated with no other hypoglycemic agents other than a stable dose (>3 months) of metformin (≥ 1.0 to ≤ 2 grams daily). We plan to enroll subjects with HbA1C between 6% and 9% (both inclusive) and with BMI 25-34.9 kg/m² (both inclusive). Post enrollment, patients will be randomized to saxagliptin 5 mg or placebo as detailed in Study Design for direct comparison between the two regimens.

Before any study procedures are performed, subjects will have the details of the study described to them, and they will be given a written informed consent document to read. Then, if subjects consent to participate in the study, they will indicate that consent by signing and dating the informed consent document in the presence of study personnel.

Recruitment: Subjects will be recruited from the local general physician patient population and General Endocrinology and Diabetes department at GWU, Medical Faculty Associates, where [name] is a clinician. All patients will receive counseling regarding the study aims and methods.

Study Design Overview: We propose a 2-arm randomized, double-masked, placebo-controlled, parallel group, longitudinal study of 12-weeks duration. (See study design below), recruited over 2.5 years. The 12 week time interval has been previously shown adequate to observe changes in biochemistry, EPCs and, importantly, PWV changes^{17-19,36}. Patients will be randomized to 2 groups:

Control, (n=20), Metformin + Lifestyle + Placebo

Treatment, (n=20) Metformin+ Lifestyle+ Saxagliptin 5mg

This proposed study is based on patients with type 2 diabetes of less than 8 years duration, who are already on Metformin (≥ 1.0 to ≤ 2 gm/d, stable dose for at least 3 months) but still remain poorly controlled with HbA1C between 6% and 9% (both inclusive), but not overtly out of control ($> 9\%$ of HbA1C). Our study design is similar to that of Fadini et al

²⁰where Sitagliptin was compared to placebo with endothelial progenitor cells as a outcome measure in patients with type 2 diabetes over 4 weeks. Though our study is over 12 weeks we do not anticipate significant drop in HbA1C in between the two groups in this relatively short time period to act as a confounding factor on CD34+ cell number, function and gene expression. Most clinical studies looking at HbA1C reduction were of a much longer duration of 6 months or above and most DPP-4 inhibitor studies are with animal EPCs where comparison with human CD34+ population is difficult to make. In one study⁵⁸ where saxagliptin was used for 12 weeks in drug-naïve type 2 diabetes patients there was placebo-subtracted HbA1c reduction noted of 0.45-0.63%. It showed mean placebo-subtracted reductions in fasting serum glucose of 20 mg/dL. From our laboratory studies of in vitro human EPC studies we do not think glucose level change of 20 mg/dL is significant enough to account for changes in EPC number, function and gene expression. However we will take this possibility into account during statistical analysis of the results between the saxagliptin and placebo groups.

Lifestyle Intervention for Type 2 diabetes patients²:

To keep uniformity within the cohort regarding lifestyle during the length of the study duration, all patients at entry will ideally receive dietary advice from the research coordinator, a diabetes educator, a registered dietitian (as per American Diabetes Association clinical guidelines²), specifically geared towards type 2 diabetes patients. They will be advised to adhere to 150 minutes of weekly aerobic exercise (50-70% of maximal heart rate) as best as possible. Patient's activity will be monitored using accelerometers and will be downloaded at regular intervals by the research coordinator.

Subjects will be taking 5.0 mg of Onglyza (saxagliptin) or placebo. We choose to use the maximum approved dose of saxagliptin in order to discern a definite effect.

Visits with outcome measurements will be scheduled for morning following overnight 10 hours fast to reduce diurnal variability, and clinical parameters will be obtained at scheduled office visits as depicted in the study schema and will be measured at each outcome visit as follows:

Week -4: Subjects will be screened and eligibility will be verified based on physical and laboratory tests. We will aim to recruit equal numbers of male and female patients will be recruited. All patients will be educated on the recommended lifestyle changes of maintaining a level of aerobic activity of 150 minutes/ week (non-supervised) and ideally receive dietary advice from the research coordinator, a diabetes educator, or a registered

dietitian (as per American Diabetes Association clinical guidelines²) specifically geared towards type 2 diabetes patients. We plan to monitor activity using accelerometers. We will allow 4 weeks for the patients to reach a steady state while implementing life style (diet and exercise) changes.

Week 0: At this stage patients will be randomized into the study. Subjects will have the first set of measurements. We will make sure that patients still meet the inclusion criteria. They will be started on medication or placebo and will be encouraged to continue 150 minutes/week of moderate physical exercise and dietary management for the remainder of the study.

Weeks 0, 6 and 12: Subjects will all have the same measurements and will continue on study medication or placebo. All primary and secondary measures as outlined before will be carried out.

- Primary Measures: CD34+ cell number, function and gene expression.
- Mononuclear cell population (day 0 of harvest) will be analyzed by FACS to obtain cell counts of different endothelial precursor lineage cells. Combinations of following cell markers will be used, such as CD34, KDR(VEGFR2), CD31, CD144 (VE-Cadherin), CD133 (a progenitor cell marker of indeterminate lineage) and CXCR4 (SDF1 α receptor)^{5,6,8,10,20,21,59}

For:

- CD34/KDR+
- CD34/ CXCR4+
- CXCR4 + CD31
- KDR + CD34
- Some of the MNC population will be put through a human CD34 magnetic bead column using Miltenyi Biotech Column to obtain CD34+ and CD34- cells. The CD34+ cells will be used for
- Colony Forming Unit Assay (CFU Assay) from mononuclear cell population (prior to magnetic bead sorting)
- Migration assay in response to SDF-1 (0, 10, 100 ng/mL) and if sufficient cells are available we will note migration in response to SDF1 (0, 10, 100 ng/mL)
- Gene expression assays: Genes analyzed will be eNOS, PECAM-1, IGF-1, VEGF-alpha, VEGFR2, SDF-1, CXCR4 (receptor for SDF1), anti-oxidants MnSOD, Catalase, Cu-Zn SOD, Glutathione Peroxidase, extracellular SOD, pro-inflammatory markers such as IL6, TNF-alpha and Endothelin-1 genes and apoptosis cascade genes such as p53, p21, Bcl-2, GPX, Caspase-3 will be analyzed.

Secondary Measures:

- Highly selective C-reactive protein (hs-CRP), IL-6, TNF-alpha, Leptin ^{,18, 28}, and fasting lipid profile
- Serum SOD activity and SDF1 alpha (ELISA), VEGF-A (ELISA) and GLP-1 (ELISA) levels will also be assessed^{14,20,24,39}.
- Assessment of insulin sensitivity using the HOMA-IR³², calculated from individual serum measures (fasting glucose (mg/dl)* insulin (μU/mL)/405) ³⁷.
- Adiposity will be measured using the Tanita Body Composition Analyzer scale, measured as percentage body fat, BMI, waist-hip ratio^{5,55}
- Fasting lipid profile will be checked as a marker of insulin resistance and lipo-toxicity at weeks 0, 6, and 12⁵.
- We also intend to acquire Pulse wave analysis and Vascular Flow using SphygmoCor CP system from ATCOR to measure central arterial pressure and arterial stiffness^{38,42}. The secondary measures are indirect measures of endothelial inflammation in early type 2 diabetes patients. ^{30, 31, 32, 55, 56, 57}.
- Urine pregnancy testing for women of child bearing potential

We will obtain a total of 85mL of peripheral blood per visit. Of these 85 mL, 60 mL will be used to obtain CD34+ cells from MNC population and 25 mL for biochemistry and serum ELISA assays.

Methodology of Cellular Measure of Endothelial Function:

This is the strongest and most direct endothelial functional parameter, yet the least explored.

Here we plan to measure stem cell precursors of endothelium in subjects with type 2 diabetes as a bio-marker of endothelial health.

Day 0: FACS Analysis for CD34/CD31/KDR/CD133/CD144+, CXCR4 cells (note percentage)

Sort MNC for CD34+ cells for Migration, Tube Formation Assay (Functional Assay)

And gene expression assays.

Functional Assay (Cellular): At Day 0, post cell sorting for CD34 + cells we will note functional assays of these cells.

[figure not shown]
We plan to look at:

- Colony Forming Unit Assay
- Migration assay in response to SDF-1 and VEGF-A.

Colony Forming Unit Assay: MNC's (prior to CD34 magnetic bead sorting) will be plated in Human Fibronectin Coated 6 well (5 million) or 12 well plates (2 million) from BD Biosciences or Millipore. Number of CFU will be determined at Day 5, post plating.

Migration property of the patient's CD34+ cells in response to SDF-1 will be assessed immediately post cell sorting on day 0 using modified Boyden chamber. Briefly, CD34+ cells (1-2x10e5) will be placed in the upper compartment, as shown below. Concentrations tested will be SADF-1 at concentrations of 0, 10, 100 ng/ml and if sufficient cells remain, VEGF-A at concentrations of 0, 20, 50 ng/mL^{12,34} dissolved in basal endothelial culture media. Other than this protocol one can also use Migration Assay kit using 3micron pore size from Cell BioLabs Inc. (catalog # CBA-103).

These tests will evaluate the functional (migration) property of CD34+ endothelial progenitor cells⁶⁰.

The CD34+ cells obtained at day 0 from peripheral blood derived mononuclear cell population will be analyzed for mRNA expression of various endothelial function related genes,

- The gene expression changes should indicate changes in paracrine properties of CD34+ cells pre and post saxagliptin therapy,
- Genes analyzed will be eNOS, and PECAM-1, VEGF, VEGFR2, SDF-1alpha, CXCR4, IGF-1^{36,42,43}. Intra-cellular antioxidant genes such as MnSOD, Catalase and GPX will also be noted^{22,23,44,45}. eNOS is a critical gene regulating EPC's nitric oxide production capability²². PECAM-1 is platelet endothelial cell adhesion molecule and indicates inflammatory potential of endothelial lineage cells. VEGF and IGF-1 are growth factors produced by healthy EPCs. MnSOD and Catalase are anti-oxidants which may be important endothelial anti-inflammatory agents and may promote healing in hyperglycemic conditions^{9,12,31,46}. Pro-inflammatory markers such as IL6, TNF-alpha and Endothelin-1 genes and apoptosis cascade genes such as p53, p21, Bcl-2, will be analyzed in addition to other genes previously mentioned.

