1.3 Research Hypothesis

We believe poor viability and function of EPCs in early diabetes ultimately affects the repair and regeneration of the endothelium and that prompt intervention using saxagliptin with another oral hypoglycemic agent, Metformin, may reduce or reverse cardiovascular risk by improving EPC survival and function above and beyond adequate glucose metabolism control.

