4 INVESTIGATIONAL PLAN

4.1 Study Design and Duration

Study Schema, 42 Type 2 diabetic Subjects Aged 40-70 on stable dose of Metformin

+/- 3 days for visits Wk 0 Wk 6 and Wk 12, if the particular day is not feasible

*Assessed at week 0, 6 and 12: Biochemical and cellular markers of endothelial function and Pulse wave analysis and velocity (PWA and PWV).

Available related studies and Expected Results: Studies measuring changes to EPCs in type 2 diabetes patients are very limited. To the best of our knowledge there are no studies examining the effect of saxagliptin in early diabetes on patient's CD34/KDR+ve cells and comparing that to the effect of lifestyle + metformin on CD34+ve cell population. The regenerative potential of EPC is thought to be due to direct incorporation into vascular endothelium and/or the secretion of angio-supportive factors to enhance endothelial repair and function^{17, 18, 19}. Our studies and others^{11, 12, 34}, have shown that various disease states, including those seen in diabetes, can deplete and damage EPC, thereby diminishing their regenerative potential. The inability to maintain or repair damaged endothelial tissue leads to cumulative vascular dysfunction and cardiovascular disease.

We hypothesize that monitoring *number, function and gene expression of endothelial progenitors will allow us to quantify cardiovascular disease risk at the onset and regenerative potential post intervention at a cellular level. It will also help us to identify and correlate the best endothelial function bio-chemical inflammatory marker as an early indicator of cardiovascular disease progression in early type 2 diabetes.*

Therefore, studying the effects of Saxagliptin which can increase SDF1 alpha levels and possibly CXCR4 receptor expression as an intervention on the number and health of EPCs may not only provide insight on the biological role of these cells, but they can be used as a tool to study vascular biology and lastly can be a potential target for prevention of diabetes vascular complications.

We expect to establish that saxagliptin improves endothelial function that is EPC number, function, gene expression and bio-inflammatory markers beyond its glycemic control effect in type 2 diabetes patients.

Saxagliptin 5 mg or placebo will be added to patients who have type 2 diabetes diagnosed less than 8 years with HbA1C of 6 to 9 % (both inclusive) while being on lifestyle modification and Metformin (≥ 1.0 to ≤ 2 gm/d orally).

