In the event that TIME is modeled using indicator variables, two indicator variables will be used to represent the three time points, with baseline serving as the reference category. The interaction between GROUP and TIME will be modeled in a similar fashion using two additional indicator variables. The above multivariable model enables us to adjust for time-varying covariates, such as glucose. Since glucose will be measured contemporaneously with the outcomes at each visit, however, causal interpretations of glucose and any outcome are suspect. As such, we will consider glucose as a nuisance covariate, and consider any relationship between glucose and an outcome as merely associative.

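### The placebo comparison can support a total effect of adding saxagliptin, not the planned conclusion of an effect beyond glycaemic control

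*Combined protocol and SAP*

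**What the plan says.** - **Claim.** Section 1.3, repeated in the Synopsis, hypothesises lower cardiovascular risk by "improving EPC survival and function above and beyond adequate glucose metabolism control". Section 4.1 turns this into an expected result: "We expect to establish that saxagliptin improves endothelial function that is EPC number, function, gene expression and bio-inflammatory markers beyond its glycemic control effect".
- **Design.** There are two arms (Section 6.2, Study Design Overview). The control is "Metformin + Lifestyle + Placebo"; the other arm has saxagliptin 5 mg in place of placebo. Metformin stays at the entry dose in both (Section 5.1).
- **Defence of the claim.** Section 6.2 states that "we do not anticipate significant drop in HbA1C in between the two groups in this relatively short time period". The sentence goes on to make clear that it means a drop that would confound the CD34+ measures. The same paragraph then cites a 12-week saxagliptin study in drug-naive patients, with a "placebo-subtracted HbA1c reduction noted of 0.45-0.63" percentage points and "mean placebo-subtracted reductions in fasting serum glucose of 20 mg/dL". It adds that in vitro work suggests 20 mg/dL is too little to explain EPC changes, and promises to allow for the possibility in the analysis.
- **Related evidence.** Section 1.1.5 reports statistically significant A1C reductions against control in the Phase 3 studies, including the add-on-to-metformin study. It gives no size and no 12-week value.
- **Analysis.** Section 8 centres on the group-by-time interaction in a linear mixed model. It allows glucose as a time-varying nuisance covariate, calls causal readings of glucose suspect, and will "consider any relationship between glucose and an outcome as merely associative".

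**The concern.** Randomisation makes the arms comparable except for what follows from saxagliptin, and glucose lowering is one of those consequences. The group-by-time contrast therefore estimates everything the drug does to EPCs, through glycaemia or otherwise. No arm lowers glucose by a similar amount by another route, so the contrast itself cannot separate the two pathways. The protocol gives its own reasons not to take the glycaemic pathway as zero: Section 1 links diabetes, as a pro-oxidative state, to EPC dysfunction, and Section 4.1 says disease states seen in diabetes deplete and damage these cells.

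The step from a total effect to an effect beyond glycaemic control thus rests on two supports: the expectation of little HbA1c separation, and the glucose-adjusted model. If neither bears the weight, a positive result could be reported as a mechanism that the trial did not identify.

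**Working it through.** **Inputs from the documents.** Section 8: slopes of 4 versus 5 cells per week, SD 15, correlation 0.60, visits at weeks 0, 6 and 12, 18 completers per group, 12 cells difference at week 12, 20 enrolled per group. Section 6.2: 0.45 to 0.63 HbA1c points and 20 mg/dL fasting glucose at 12 weeks.

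**Assumed, not in the documents.** SD of HbA1c 0.6 to 1.0 points; SD of glucose 30 to 40 mg/dL; correlation of EPC count with glycaemia 0.1 to 0.5.

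**1. What the stated power refers to.**

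SE of the slope difference = √(2 × SD² × (1 − ρ) / (n × Sxx)), with Sxx = 36 + 0 + 36 = 72.

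SE = √(2 × 225 × 0.40 / (18 × 72)) = √(180/1296) = 0.373 cells per week.

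Power = Φ(1/0.373 − 1.645) = 85.0% with one-sided 0.05, against the stated 84%. Two-sided 0.05 gives 76.5%; the plan does not state sidedness, which is a separate matter. The figure concerns the total slope difference. No power is given for a glucose-independent component.

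**2. The premise beside its citation.** If the cited HbA1c effect carried over, the chance of a significant difference with 20 per group (two-sided 0.05) is Φ(δ / (SD × √(2/20)) − 1.96):

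| δ (points) | SD 0.6 | SD 1.0 |
|---|---|---|
| 0.45 | 66% | 30% |
| 0.63 | 91% | 51% |

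A non-significant HbA1c comparison in this trial would therefore not show that glycaemia was equal in the two arms.

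**3. How much could run through glycaemia.** To explain all 12 cells, glycaemia would need 12/20 = 0.6 cells per mg/dL, or 12/0.63 = 19 to 12/0.45 = 27 cells per HbA1c point. Under the assumed ranges:

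- Through glucose, r × (15/SD) × 20: from 0.1 × 15/40 × 20 = 0.75 to 0.5 × 15/30 × 20 = 5.0 cells (6 to 42% of 12).
- Through HbA1c, r × (15/SD) × δ: from 0.1 × 15/1.0 × 0.45 = 0.7 to 0.5 × 15/0.6 × 0.63 = 7.9 cells (6 to 66% of 12).

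With no direct effect at all, the group-by-time test (18 per group, two-sided 0.05) would then be significant in about 5 to 20% of trials (glucose) or 5 to 42% (HbA1c).

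**4. What glucose adjustment recovers.** Take a true direct effect of zero and an unmeasured factor correlated r_G with glucose change and r_E with EPC change. Using glucose SD 30 and correlation 0.60 for both variables, the SDs of change are 30 × √0.8 = 26.8 mg/dL and 15 × √0.8 = 13.4 cells, a ratio of 0.5. The adjusted group difference is shifted by r_G × r_E × 0.5 × 20:

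| r_G, r_E | Formula | Simulated (week-12 changes, 400,000 per arm) |
|---|---|---|
| 0, 0 | 0 | −0.01 |
| 0.5, 0.5 | +2.5 | +2.51 |
| 0.5, −0.5 | −2.5 | −2.58 |
| 0.7, 0.7 | +4.9 | +4.88 |

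The adjustment is right when there is no shared cause. Otherwise it can err in either direction.

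**5. What is adjusted for.** Outcome visits follow a 10-hour fast (Section 6.2), so the glucose measured alongside the outcomes is fasting glucose. Section 1.1.5 reports that saxagliptin also lowers postprandial glucose and A1C. Section 8 does not name HbA1c as a covariate. Any glycaemic effect that fasting glucose does not carry would stay in the group term.

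**The case against.** Five points can be made for the plan.

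- **The premise is qualified and the counter-evidence disclosed.** Section 6.2 speaks of a drop large enough to confound, then cites the 12-week figures itself and adds the in vitro argument. This stands. The in vitro data are not shown, so the argument can be neither relied on nor called wrong; it addresses the 20 mg/dL change and not HbA1c.
- **The cited patients differ.** They were drug-naive, whereas these take metformin with HbA1c from 6%. This stands: a reader might infer that the citation contradicts the premise outright, but the documents give no 12-week effect for add-on to metformin.
- **The plan does not rely on the placebo contrast alone.** This also stands. A reader might infer that no planned analysis could address glucose independence. Section 8 does allow glucose adjustment, and step 4 shows that it recovers the right answer under one condition. Its caveat concerns the glucose-outcome relationship and does not make the adjusted group term worthless. What is missing is a statement of that condition.
- **The formal objective is already a total effect.** The Synopsis asks whether adding saxagliptin improves endothelial dysfunction, and Section 1.3 is worded as a belief. True, but Section 4.1 says the trial is expected to establish the stronger claim.
- **The illustrated shares rest on outside assumptions.** Agreed. They show what is possible and do not estimate what will happen.

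**Conclusion.** The expected conclusion in Section 4.1 goes beyond what the design identifies and should be reworded. The total effect of adding saxagliptin is identified by randomisation. An effect beyond glycaemic control requires that glucose change and EPC change share no unmeasured cause, and that the measured glucose captures the glycaemic pathway. The plan states neither, post-baseline glucose is itself affected by treatment, and Section 8 disclaims causal interpretation.

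On the protocol's own citation, the separation to expect is 0.45 to 0.63 HbA1c points and 20 mg/dL, subject to the drug-naive caveat. With moderate to strong shared causes (correlations 0.5 to 0.7, assumed), the adjusted estimate would be off by about 2.5 to 4.9 cells against a 12-cell target.

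Two further inferences are not supported. A reader might set the HbA1c difference against the width of the entry range to call it large, but an eligibility range is not a scale of EPC relevance. A reader might also infer that glycaemia would explain the whole effect; the documents give no EPC-glycaemia relationship, and under the assumed ranges it explains part of it. The main group-by-time test, taken as a test of the total effect, is not put in doubt by this point.

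**What to change.** 1. **Section 4.1**, and the Synopsis and Section 1.3 wherever their hypothesis is used as a conclusion: state the confirmatory conclusion as the total effect of adding saxagliptin 5 mg to metformin plus lifestyle. Keep the idea of benefit beyond glycaemic control as an exploratory hypothesis.
2. **Section 8:** specify that the confirmatory group-by-time test excludes post-baseline glucose. Present any glucose-adjusted model as hypothesis-generating, with the no-unmeasured-confounding assumption written out.
3. **Section 6.2:** replace the premise about HbA1c with the cited 12-week expectation (0.45 to 0.63 points, 20 mg/dL) and note that those patients were drug-naive.
4. **Reporting:** give the between-arm differences in HbA1c and fasting glucose, with confidence intervals, beside the CD34+ result.

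No new arm, patients or data are needed. Section 2.2 already lists HbA1c and fasting glucose, and Section 6.2 calls for all secondary measures at weeks 0, 6 and 12. Its itemised list does not repeat HbA1c, so it should be named there. The cost is a narrower claim.
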